## Sample size calculations overview

		Protocol	Randomisation
Minimum Detectable Effect Size (MDES)		Standardised mean difference = 0.15	Standardised mean difference = 0.17
Pre-test/ post-test correlations	level 1 (participant)	-	-
	level 2 (cluster)	-	-
Intracluster correlations (ICCs)	level 1 (participant)	0.03	0.041
	level 3 (cluster)	-	-
Alpha		0.05	0.05
Power		0.8	0.8
One-sided or two-sided?		Two-sided	Two-sided
Average cluster size		186 pupils 159 staff	220 pupils 26 staff
Number of clusters	intervention	29	31
	control	29	31
	total	58	62

		Protocol	Randomisation
Number of participants	intervention	4650 pupils 3975 staff	6429 pupils 724 staff
	control	4650 pupils 3975 staff	7194 pupils 896 staff
	total	9300 pupils 7950 staff	13623 pupils 1620 staff

The cluster sample size was determined a priori using a minimum detectable effect size (MDES) of 0.15 (standardised mean difference). The protocol presented different scenarios for sample size calculations based on a MDES between 0.10 and 0.20 (see Table 4 in the trial protocol). Presented in the table above is the sample size calculation for MDES of 0.15, which is in line with a projected school recruitment of 55 schools inflated to account for 15% attrition (58 in total). The estimate for the mean and SD of externalising difficulties in the control arm was based on the combined female and male scores from Elia et al. (2020). The intraclass correlation coefficient was assumed as 0.03. There is a lack of evidence on which to base assumptions for the pre-post correlation of externalising difficulties, so the sample size calculations were not adjusted to account for this. STATA was used for the power calculation using the following code: (MDE 0.15) power twomeans 5.21 4.76, sd(2.96) rho(0.03) m1(186) m2(186) power(0.8) cvcluster(0.5) cluster = 25 schools and 4,650 pupils per arm (increased to 29 schools per arm based on 15% school attrition).

The primary population of interest is pupils; estimates are also presented for staff. The pupil and staff sample sizes were determined from figures from three initial Local Authorities (LAs; Kent, Slough and Wiltshire). From this, 186 pupils per school were assumed after accounting for 35% study refusal and 25% attrition, resulting in an estimated sample size of 9300 pupils in total. 159 staff per schools were assumed after accounting for 35% study refusal and 25% attrition, resulting in 7950 staff in total.

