The section with actual sample size and MDES at randomisation were updated following randomisation in February 2024. The average cluster size for pupils who completed the

primary outcome (SDQ externalising symptoms items) was 219.73, rounded to 220 pupils in the table. Furthermore, intracluster correlation was calculated as 0.041 and coefficient of variation was 0.366. With these parameters, we are powered to detect MDES of 0.17. Please see the following STATA code, which estimates the number of schools as 24.3 and the number of pupils per arm as 5333.02, inflated to 29 schools and 6372 pupils per arm based on 15% school attrition: `power twomeans 5.21 4.7, sd(2.96) rho(0.041) m1(219.73) m2(219.73) power(0.8) cvcluster(0.366) nfrac display "schools per arm = " ceil(r(K1)/.85) display "pupils per arm = " round(ceil(r(K1)/.85)*219.73).`

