## Analysis

Analyses will be conducted by an analyst masked to intervention group assignment following the intention-to-treat principle. The hypotheses and general analysis framework were decided a priori; the analysis plan was written and finalised during the period of data collection after recruitment but before baseline data collection was completed. The analyses will use maximum likelihood estimation meaning all participants will be included, even those with missing follow up data points, in line with the intention-to-treat principle. There will be two approaches to handling missing data, assuming that data are missing at random: 1) multiple imputation of data at any time point using wide format data, and 2) participants who have at least one post-randomisation observation will be included in the model with maximum likelihood estimation. Results will be compared using the two approaches. The chosen analysis model to assess the intervention effect is a mixed effects model. This model will form the basis of the main trial report that will be submitted for publication. Fixed effects will include group allocation (intervention/control), time (mid-programme/end of programme), and the interaction between group allocation and time. Random intercepts for pupils or staff nested within schools will also be specified, depending on whether the outcome is pupil- or staff-specific. The baseline level of the outcome will be included as a covariate to increase power and precision. Cohort (1/2), year group (8/9) and gender (dummy coded: male/female/gender diverse, reference: male) will be included as fixed effect prognostic factors to improve precision of the treatment effect. LA/CA was used as a stratifier in the randomisation, and it is intended to be included in the analysis as a fixed effect. However, there may be issues with model estimation due to a small number of schools per LA/CA (minimum of two). In this case, we will specify a three-level model (pupil, school, LA) or remove LA/CA as a fixed effect from the analysis. For the mixed effects models, the package *lme4* version (version 1.1-35.1) in R will be used (Bates et al., 2015). Interaction terms will be specified within the mixed effects models. Example syntax for the primary outcome of pupil externalising symptoms with LA/CA included as a fixed effect is:

```

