### **Secondary outcome analysis**

Additional pupil outcomes will be included as part of the secondary outcome analysis. The same model specification will be used as for the primary outcome, and separate models will be specified for each of the outcomes. All outcomes are measured at baseline, mid-programme, and end of programme, unless otherwise specified.

- Internalising difficulties measured using the sum score of emotional symptoms and peer problems sub-scales of the Strengths and Difficulties Questionnaire (SDQ; Goodman et al., 1998)
- Impact of mental health difficulties measured using the impact score of the SDQ
- Prosocial behaviour measured using the prosocial behaviour subscale of the SDQ
- Teacher-student relationships measured using the teacher-student relationships subscale of the Student Engagement Instrument (SEI; Appleton et al., 2006)
- Peer support for learning measured using the peer support for learning subscale of the SEI
- Control and relevance of school work measured using the control and relevance of school work subscale of the SEI
- Future aspirations and goals measured using the future aspirations and goals subscale of the SEI
- Bullying perpetration measured using the bullying perpetration subscale of the Illinois Bully Scale (IBS; Espelage & Holt, 2001)
- Bullying victimisation measured using the bullying victimisation subscale of the IBS
- School attendance using local school data at mid-programme and end-of-programme
- School exclusions using local school data at mid-programme and end-of-programme
- Permanent school exclusions using local school data at mid-programme and end-of-programme
- Longer-term school attendance will be measured using data from the National Pupil Database after winter 2025
- Longer-term school exclusions will be measured using data from the National Pupil Database after winter 2025
- Longer-term permanent school exclusions will be measured using data from the National Pupil Database after winter 2025
- Academic attainment will be measured using Key Stage 4 attainment after winter 2025.

Staff secondary outcome analysis will follow the same specification as the primary outcome analysis, except that the random intercept will be staff nested within schools. All outcomes are measured at baseline, mid-programme, and end of programme, unless otherwise specified.

The following outcomes will be considered in separate models:

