### **Presentation of outcomes**

Standardised mean difference will be used to calculate the effect size. Total variance will be used in the calculation of the effect size, to account for the nested structure of the data.

The exact specification of the numerator and denominator is detailed below:

- Numerator = Adjusted mean difference estimate at each time point from the primary intervention effect analysis described above
- Denominator = Pooled unconditional variance for both intervention and control groups.

Bootstrapped confidence intervals will be used to reflect statistical uncertainty.

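### No version of the primary model lets a school's deviation change between visits, so under the text model the pupil group-by-time test is too liberal unless schools are perfectly stable; the time-point effects are little affected

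*SAP*

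**What the plan says.** The Analysis section of the SAP lists as fixed effects group, time (mid-programme or end of programme) and "the interaction between group allocation and time". For the random part it says "Random intercepts for pupils or staff nested within schools will also be specified".

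The model is given in two further forms:
- The example syntax at the end of the opening part of Analysis has one random term, grouped by pupil.
- The equation under Primary outcome analysis has school and LA/CA intercepts without a time index, and no pupil intercept.

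Under Secondary outcome analysis, "The same model specification will be used as for the primary outcome" for the other pupil outcomes; the staff outcomes follow it with staff in place of pupils. Presentation of outcomes defines the numerator of the effect size as "Adjusted mean difference estimate at each time point from the primary intervention effect analysis described above", with bootstrapped confidence intervals. It does not state the resampling unit.

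**The concern.** The two follow-up visits are about 11 months apart in each cohort (April 2024 to March 2025, and July 2024 to June 2025, under Longitudinal follow-up analyses). Over that time a school's mean may move for reasons unrelated to the programme, such as staff turnover, local events or survey conditions. None of the three specifications has a term for this.

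Under the text model, movement shared by all pupils of a school is treated as if it averaged out over individual pupils. The interaction test then asks whether any school changed differently from the others, when the question is whether the training effect differs between visits.

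The interaction would support any statement that the effect builds up or fades as training is completed. It belongs to the model on which the main trial report is to be based, and it is carried to the secondary outcomes.

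**Working it through.** **The plan's own figure.** The randomisation-stage calculation is "power twomeans 5.21 4.7, sd(2.96) rho(0.041) m1(219.73) m2(219.73", with power 0.8 and CV of cluster size 0.366.
- Individual n per arm = 2[2.96(1.960 + 0.842)/0.51]² = 528.8.
- Design effect = 1 + 218.73 × 0.041 = 9.968, so 528.8 × 9.968/219.73 = 23.99 schools.
- Unequal sizes: L = m·ICC/(1 − ICC + m·ICC) = 0.904, and the factor 1/(1 − CV²·L(1 − L)) = 1.0118 gives 24.27 schools and 5,333 pupils per arm.
- Dividing by 0.85 and rounding up gives 29 schools and 6,372 pupils.

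This reproduces the SAP.

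**Inputs for the interaction test.** From the SAP: 31 schools per arm, ICC 0.041, CV 0.366, two-sided 5%, and m = 220 pupils per school, or 165 after the planned 25% attrition (220 × 0.75). Assumed, because the SAP gives no value: pupil correlation between visits ρ = 0.6 to 0.7; school correlation between visits r = 0.80 to 1; and an ICC of 0.02 as an alternative after covariate adjustment.

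**Formula.** With two visits and complete data, the text model's interaction test equals a pupil-level test of change scores. On the scale of total variance 1, let e = (1 − ICC)(1 − ρ) and s = ICC(1 − r). The ratio of true to model-based variance is

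R = [e/m + s(1 + CV²)] / [(e + s)/m], and the true size is 2[1 − Φ(1.96/√R)].

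**Example.** ICC 0.041, m = 220, ρ = 0.6, r = 0.95: e = 0.3836 and s = 0.00205. R = (0.3836 + 220 × 0.00205 × 1.134)/(0.3836 + 0.00205) = 0.8950/0.38565 = 2.32. The standard error is too small by a factor of 1.52 and the size is 20%.

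**Type I error (%), pupils, text model:**

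| ICC | r | m 220, ρ 0.6 | m 220, ρ 0.7 | m 165, ρ 0.6 | m 165, ρ 0.7 |
|---|---|---|---|---|---|
| 0.041 | 1.00 | 5 | 5 | 5 | 5 |
| 0.041 | 0.98 | 11 | 13 | 10 | 11 |
| 0.041 | 0.95 | 20 | 24 | 16 | 20 |
| 0.041 | 0.90 | 30 | 36 | 26 | 30 |
| 0.041 | 0.80 | 43 | 49 | 38 | 43 |
| 0.02 | 0.95 | 13 | 15 | 11 | 12 |
| 0.02 | 0.90 | 19 | 23 | 16 | 19 |
| 0.02 | 0.80 | 30 | 35 | 25 | 29 |

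As a check, 4,000 simulated trials per setting (equal schools of 220, ICC 0.041, pupil residual variance 0.30) gave 5.5% at r = 1, 21% at 0.95, 33% at 0.90 and 46% at 0.80. A school-level test of change, which allows for school drift, stayed at 4.1-5.6% in the simulations with the inputs above.

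**How much drift this is.** At r = 0.95 the SD of a school's mid-to-end change is √(2 × 0.041 × 0.05) = 0.064 pupil SDs. With the SD of about 4.23 in Table 1 that is 0.27 SDQ points, well below the MDES of 0.17 SDs.

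**Model equation (no pupil intercept).** The residual then holds all within-school variance, so the denominator of R becomes (1 − ICC + s)/m. At ICC 0.041 and the same ρ and m, the size is 2-4%, 6-10% and 15-22% at r = 0.95, 0.90 and 0.80.

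**Staff.** With m = 26, an assumed ICC of 0.041, residual variance 0.30 and equal clusters, R = 1.17, 1.34 and 1.67, and the size is 7.0%, 9.0% and 12.9% at the same r.

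**Difference at one time point.** The school intercept stays in this standard error. The model takes the school variance as about ICC(1 + r)/2 where the truth is ICC, so the variance is understated by at most about 2/(1 + r). That is 1.026, 1.053 and 1.111 at r = 0.95, 0.90 and 0.80, or sizes of 5.3%, 5.6% and 6.3%. Across all simulations the range was about 5-8%.

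**The case against.** The strongest reply is that the reported effect is hardly touched. The SAP does not name the interaction as the deciding test; it reports the difference at each time point. A reader might infer from the table that the trial's primary comparison has a false-positive rate of 20-45%. The SAP does not support that, and this part of the reply stands in full.

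Three further points also stand:
- The rates are not properties of the SAP. They need r below 1 and a value for ρ, and the SAP gives neither. The ICC of 0.041 was calculated at baseline, whereas the model adjusts for the baseline outcome, cohort, year group, gender and, if feasible, LA/CA, so the remaining school variance may be smaller.
- The high rates belong to the text model. Under the model equation the test can even be conservative. That comes from a second omission working the other way, so it is no safeguard, and it conflicts with the text.
- The pupil rates must not be carried over to staff, where clusters are far smaller.

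One might also conclude that the time-point intervals are too narrow. That is not established. A bootstrap that resamples whole schools would largely capture school drift, while a parametric bootstrap from the planned model would not, and the SAP does not say which is meant.

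None of this supplies the missing term. The text model still holds its level for the interaction only at r = 1.

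**Conclusion.** The point holds in a conditional form. No specification in the SAP has a school-by-time random effect. Under the text model the pupil group-by-time test is therefore anti-conservative whenever school deviations are less than perfectly correlated between visits. The size depends on quantities that the SAP does not give: 5% at r = 1; 16-49% for r from 0.95 to 0.80 at ICC 0.041; and 11-35% at ICC 0.02, all for an assumed ρ of 0.6 to 0.7. The omission is certain; the figures are only as good as these assumptions. The consequence is confined mainly to claims that the effect grows or fades. It does not undermine the effect reported at each time point, so this is a worthwhile correction and no threat to the headline result.

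**What to change.** The text, the example syntax and the equation have to be brought into agreement in any case. When that is done, add a school-by-time random intercept to the repeated-measures models for pupils and staff, for example `(1 | school) + (1 | school:time) + (1 | school:pupil)`, or an unstructured 2 × 2 school-by-time covariance. Take both the group-by-time test and the time-point tests from that model. State the resampling unit of the bootstrap in the same revision.

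The cost is a line of SAP text and one more term in the code, with no new data. The model gains one variance component, which may sometimes be estimated at zero, and the intervals become slightly wider. If schools are in fact stable, the component falls near zero and little is lost.

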## Introduction

More Good Days At School (MGDAS) is a two-arm cluster randomised controlled trial. The trial is an evaluation of a whole-school trauma-informed practice programme, which focuses on training and capacity building for all school staff in understanding the impact of trauma, the importance of staff-pupil relationships, relational approaches, and strategies to look after one's own mental health.

The school is the unit of randomisation: half of the schools were randomised to receive the training, and half were to continue with existing wellbeing support practices at the school. The evaluation is focused on year 8 pupils, year 9 pupils and school staff. Schools were randomised in two cohorts: cohort 1 in November 2023 and cohort 2 in February 2024. Randomisation was stratified by Local Authority (LA) or Combined Authority (CA), with a minimum of two schools needed for LA/CA to be included in the randomisation.

There are three data collection periods: baseline, mid-programme (approximately 5 months after randomisation), and end of programme (after training is complete: approximately 16 months after randomisation). Data collection periods were coordinated between cohorts so that they occurred at the same stages for training inputs.

The primary outcome measure is externalising difficulties, as measured by the sum score of the conduct problems and hyperactivity subscales of the Strengths and Difficulties Questionnaire (Goodman et al., 1998). Secondary outcome measures are related to pupil and teacher wellbeing and school connections; the variables and measures are listed in detail in the Design Overview.

The main purpose of the analysis is to evaluate the impact of whole-school trauma-informed practice training on primary and secondary outcome measures for staff and pupils. Additional analyses will be conducted to test for differential effects of whole-school trauma-informed practice training, such whether the effect of training differs by ethnicity, free school meal (FSM) eligibility, special educational needs and disabilities (SEND) or Education, Health and Care Plan (EHCP) status, year group, and staff-reported empathy and control. In addition, analyses will be conducted to clarify the mechanisms by which training impacts pupil outcomes, such whether safe social connections with teachers mediates the relationship between training and pupil's externalising difficulties.

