lmer(externalising ~ group * time + (1 + school | pupil) + baseline_externalising + cohort_1_2 + year_group_8_9 + male_female + male_diverse + LA_CA, data = MGDAS_data)
```

Subgroup analyses and further analyses are detailed in the relevant sections below.

Standard data quality checks will be performed in the data preparation stage before analysis, including impossible values, distribution of scores and residuals, outliers, low frequency categorical variables, linearity, and homogeneity of variance. Violations will be managed with

appropriate techniques. Descriptive statistics of the implementation data will be used to identify levels of implementation and engagement.

There are no planned interim analyses for efficacy.

This project contains multiple secondary outcomes and analyses. For pupils, there are 16 secondary outcomes, and, for staff, there are 7 secondary outcomes. As a result, there is a higher risk of false positives overall. To mitigate this, false discovery rate (FDR) multiple comparison correction will be applied to the significance level for tests for outcomes that are within the same measure, as these are likely to be correlated both theoretically and statistically. For example, FDR correction will be applied to three SDQ secondary pupil outcomes. In a similar vein, FDR correction will be applied to subgroup and further analyses. Some of these analyses will be underpowered, increasing the chance of false negatives in some cases. All exploratory analyses must therefore be treated with caution and not interpreted individually.

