### **Primary outcome analysis**

The primary outcome is externalising difficulties measured using the conduct problems and hyperactivity subscales of the Strengths and Difficulties Questionnaire (Goodman et al., 1998). It will be included in the model as one total score (Goodman et al., 2010).

The model will have three levels, nesting pupil within school, and school within LA/CA. These will be fixed effects due to this being an efficacy trial, as well as the small number (minimum 2) of schools within each LA/CA. Given the small number of schools nested within each LA/CA, this top level of nesting may be adjusted or removed from the model.

For pupil (i) in school (j) in LA/CA (k), we define the model as:

$$\begin{aligned} (\text{Externalising difficulties}_{ijk}) = & \beta_0 + \beta_1(\text{group allocation}_{jk}) + \beta_2(\text{measurement time}_{jk}) + \beta_3(\text{group} \\ & \text{allocation}_{jk}) * (\text{measurement time}_{jk}) + \beta_4(\text{cohort}_{jk}) + \beta_5(\text{year group}_{ijk}) + \beta_6(\text{gender}_{ijk}) + u_{0jk} + v_{0k} \\ & + e_{ijk} \end{aligned}$$

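### The example lmer call for the primary outcome has no school random intercept, contradicts the SAP's own nested model, and will not run under lme4 defaults

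*SAP*

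**What the plan says.** The Introduction makes the design plain: "The school is the unit of randomisation", and "half of the schools were randomised to receive the training". The Analysis section then describes a mixed model: "Random intercepts for pupils or staff nested within schools will also be specified", with the baseline level of the outcome as a covariate and LA/CA intended as a fixed effect. The same section gives example syntax for the primary outcome, which begins "lmer(externalising ~ group * time + (1 + school | pupil) + baseline_externalising" and goes on to list fixed covariates, including LA/CA. The term in brackets is the only random term in the call.

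The Primary outcome analysis section states "The model will have three levels, nesting pupil within school, and school within LA/CA". It then describes these as fixed effects, yet its equation carries a school term u_0jk and an LA/CA term v_0k. That equation has neither a pupil random intercept nor the baseline score.

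**The concern.** In a school-randomised trial the comparison between arms must be judged against variation between schools. The sample size allows for this through a school ICC. The written call has no variance component for school, and the LA/CA fixed effect cannot replace one, because it does not make pupils of the same school correlated within an LA/CA.

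The slope for school within pupil has no meaning here: a pupil attends one school, so slope and intercept cannot be separated within any pupil.

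Prose, equation and code therefore give three different models for the primary outcome. Whoever runs the call will have to choose a replacement once follow-up data exist. One easy repair, dropping the slope, would leave a model that runs but ignores the clusters.

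**Working it through.** **Inputs from the SAP**

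- 31 schools per arm, 62 in total (Sample size calculations overview; Table 1).
- "13623 pupils 1620 staff" at randomisation (Sample size calculations overview).
- At most two outcome rows per pupil: time enters as "time (mid-programme/end of programme", and baseline is a covariate (Analysis).
- ICC 0.041, mean cluster size m = 219.73, cluster-size CV 0.366, difference 5.21 − 4.70 = 0.51, SD 2.96, two-sided alpha 0.05, power 0.8 (Sample size calculations overview).

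**1. The SAP's own figure, which does allow for clustering**

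- Pupils per arm without clustering: 2 × (2.96 × (1.960 + 0.842) / 0.51)² = 528.8.
- Design effect: 1 + (219.73 − 1) × 0.041 = 9.97.
- Unequal cluster sizes: L = mρ / (mρ + 1 − ρ) = 9.009 / 9.968 = 0.904. Relative efficiency = 1 − 0.366² × 0.904 × 0.096 = 0.988.
- Result: 528.8 × 9.97 / 0.988 gives 5333 pupils and 24.27 schools per arm. Dividing by 0.85 and rounding up gives 29 schools and 29 × 219.73 = 6372 pupils.

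This matches the stated 24.3 schools and 5333.02 pupils, then 29 and 6372. The sample size is sound on this point and presumes an analysis with a school component.

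**2. Can the call run?**

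- Rows: at most 2 × 13,623 = 27,246.
- School numeric: intercept plus one slope per pupil, 2 × 13,623 = 27,246 random effects.
- School as a factor: intercept plus 61 contrasts per pupil, 62 × 13,623 = 844,626 random effects, with 62 × 63 / 2 = 1,953 covariance parameters.

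lme4 stops by default when rows do not exceed the random effects of a term. With two or more random effects and at most two rows per pupil, this holds for any number of pupils. Both codings were run in lme4 1.1-37 (the SAP names 1.1-35.1) on simulated data with 20 schools, 40 pupils each and two time points. Both stopped with that message.

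**3. What if the check is switched off?**

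On the same simulated data the numeric version ran with a convergence warning and returned pupil-level components only. The standard error of the group coefficient was 0.067, against 0.081 with `(1 | school) + (1 | pupil)`. The group-by-time standard error barely moved (0.0636 against 0.0637), because a constant school intercept cancels from a change over time. The loss therefore falls on the difference between arms at a time point, which is the effect named under Presentation of outcomes.

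**4. Size at the trial's own parameters, if clustering is ignored**

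Type I error = 2 × (1 − Φ(1.96 / √DEFF)).

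| ICC | DEFF | SE too small by | Type I error |
|---|---|---|---|
| 0.041 (SAP) | 9.97 | 3.16 | 0.53 |
| 0.02 (assumed) | 5.37 | 2.32 | 0.40 |
| 0.01 (assumed) | 3.19 | 1.79 | 0.27 |

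Allowing for the cluster-size CV of 0.366 raises the first row to DEFF 11.17 and 0.56. A simulation of 4,000 null trials with 62 schools at ICC 0.041 rejected in 54% when clustering was ignored, and in 4% with a school-level analysis.

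**The case against.** The strongest reply is that the line is only an example and that the intent is clear elsewhere: the prose nests pupils in schools, the equation has a school term, ICCs are promised for all models, and the trial is powered on a school ICC. This stands as to intent. It does not settle the model, because the Primary outcome analysis section calls the levels fixed effects and its equation lacks the pupil intercept and the baseline score.

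A second reply is that a call which fails will be noticed. That is likely, and it limits the harm. The replacement would still be chosen after follow-up data exist, and `(1 | pupil)` would run without complaint.

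Three stronger readings are tempting but not supported:

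- *The planned analysis has a 53% type I error.* By default the call gives no result at all. The 53% needs the check to be overridden or the term to be shortened. It also uses the ICC reported at randomisation, not one conditional on baseline score, gender and LA/CA.
- *Every secondary outcome inherits the error.* The Secondary outcome analysis section carries over the model specification, not the code line, and for staff it restates the nesting within schools.
- *The line also shows a wrong choice of maximum likelihood over REML, or a harmful lack of a school-by-time effect.* The sentence "The analyses will use maximum likelihood estimation meaning all participants will be included, even those with missing follow up data points" explains how incomplete cases stay in the model, and the call as written would use REML. Putting a size on either issue needs a z-test, a number of LA/CAs, or correlations over time that the SAP does not give.

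**Conclusion.** The random term is wrong as written and contradicts the SAP's own text and sample size. This rests on lme4 syntax and a count of rows, not on any assumption about the data. The immediate consequence is a call that stops under default settings, with either coding of school.

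The inflated error rate is conditional. If the call is forced to run, or cut to a pupil intercept, the group difference is tested with a standard error about 3.2 times too small and a type I error of about 53% at ICC 0.041, or about 27% at an assumed conditional ICC of 0.01. The sample size is unaffected. The line should be corrected before the analysis is run, because it is the only code the SAP gives for the primary outcome of a cluster-randomised trial.

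**What to change.** In the example call, replace the random term with `(1 | school/pupil)`, equivalently `(1 | school) + (1 | school:pupil)`. For staff outcomes use staff in place of pupil.

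In the Primary outcome analysis section, remove the description of the levels as fixed effects for pupil and school, and add the pupil random intercept and the baseline covariate to the equation. Prose, equation and code will then agree on the pupil and school structure.

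A school-by-time random effect, and REML with small-sample degrees of freedom, are optional refinements and not part of this error.

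The cost is one line of code, a few sentences and a revised equation, with no new data. Standard errors will be larger than a forced run of the present call would give, and will carry the clustering that the sample size already allows for.
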